## **15.2 Sample Size/Accrual Rate**

With a maximum of 20 patients per stratum, up to 300 evaluable patients may be treated in specific arms. All patients in the ‘other’ (NOS) stratum will be evaluated and have their data analyzed by disease and type of treatment to the extent possible. As they are considered entirely exploratory, no specific targets for accrual will be used for the patients in the ‘other’ (NOS) stratum. For the secondary objective of determining the frequency of *EGFR* germline mutations in families with high susceptibility to lung cancer, we plan to enroll 15 families over a period of a year; however, specific accrual targets are not provided due to the exploratory nature of this endpoint.

In order to enroll up to 300 patients in the specific arms on the basis of molecular profiling results, it is anticipated that based on the rates of mutations that occur in the genes used for treatment assignments, approximately 600 patients may need to be enrolled onto the trial. It is anticipated that up to 10 patients per month may be enrolled onto this trial from all participating sites and in all diseases combined, and thus approximately five years may be required to enroll up to 600 patients. Far fewer patients may be enrolled if the treatments fail to allow accrual to the second stage of the trial or if some arms close to accrual due to feasibility issues.

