### 3.5 Inclusion of Women and Minorities

Both men and women of all races and ethnic groups are eligible for this trial. The following are our accrual targets based on race and gender for allhistology groups combined (i.e. NSCLC, SCLC, and thymic malignancies):

Accrual Targets				
Ethnic Category	Sex/Gender			
	Females	Males	Total	
Hispanic or Latino	42	42	=	84
Not Hispanic or Latino	258	258	=	516
Ethnic Category: Total of all subjects	300	300	=	600
Racial Category				
American Indian or Alaskan Native	12	12	=	24
Asian	90	90	=	180
Black or African American	42	42	=	84
Native Hawaiian or other Pacific Islander	12	12	=	24
White	144	144	=	288
Racial Category: Total of all subjects	300	300	=	600

Accrual Rate: 10 patients/month

Total Expected Accrual: 600 patients from all participating sites and in all diseases combined.

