## 5.3 Enrollment in treatment arms

**Treatment arms are no longer recruiting as of 3/22/16.**

Due to the rapidly progressing course of the thoracic malignancies in this study, treatment decisions will be made in approximately 2 weeks from the time that the tumor samples were obtained. Based on the molecular profiling results, the patients will be offered enrollment into a specific treatment arm according to the decision tree shown in [Figure 2](#) and the eligibility criteria described in [Section 3](#).

Individuals who meet the eligibility criteria for *EGFR* germline mutation testing ([Section 3.4](#)) but who do not have advanced cancer as defined in [Section 3.1.1](#) are not eligible for the treatment arms.

Figure 2. Schema

\* See Sections 3.2 and 3.3 for eligibility criteria for the treatment arms. Patients will be allowed to crossover to different treatment arms as long as they meet eligibility criteria.

† See separate eligibility criteria (Section 3.4) and schema for EGFR germline mutation testing.

No = No or not available

Amp = gene amplification by FISH

NOS = non-otherwise specified arm

**A** = optional re-biopsy for patients that responded to previous line of therapy

Each study arm is independent from the other arms; it has its own eligibility criteria (Section 3) and statistical considerations (Section 15), and will be analyzed independently. Additionally, it is not our intention to compare the outcomes among treatment arms since the patients enrolled in each arm will have different molecular characteristics.

Patients enrolled in one of the treatment arms of this protocol, with the exception of the NOS arm and individuals enrolled for EGFR germline mutation testing only, will be treated and

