#### **5.4 Treatment after disease progression**

Patients who initially had a response to treatment or a prolonged stabilization of the tumor (>6 months) but that eventually develop progressive disease, will be offered the option to have a repeat biopsy for molecular profiling analyses. This biopsy will have the intention to study potential mechanisms of resistance to specific targeted therapies. This will also be potentially used for treatment decisions or enrollment in other molecularly targeted protocols. However, if the patient refuses this option, we will use the most recent results of the molecular profiling analyses to verify eligibility for enrollment in an alternative treatment arm on this study (crossover).

At the time of disease progression, the patients will be allowed to re-register onto another treatment arm that is available in this protocol, according to the schema, and as long as they still meet the eligibility criteria described in Section 3. In this case, patients will be re-registered onto the treatment arm, but not re-consented. The patient will count as a new patient to that specific arm, keeping their original patient ID number.

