## **15 STATISTICAL CONSIDERATIONS**

### **15.1 Study Design/Endpoints**

The primary objectives of this study are to determine the feasibility and efficacy of the use of molecular profile directed therapies in the treatment of advanced thoracic malignancies. The feasibility rate for the trial will be evaluated by determining the percentage of enrolled patients with a successful molecular profile determined. Efficacy will be determined by assessing if patients who have treatment assigned on the basis of their molecular profiling results will exhibit reasonable response rates to the drug selected for their particular profile.

Patients with NSCLC, SCLC, and thymic malignancies will be eligible for enrollment and each will be considered a separate cohort. In addition, on the basis of the molecular profiling results, one of 5 specific treatments could be assigned to each patient. The particular treatment assignments will be made according to a cascading schema as shown. If no profile of one of the 5 types listed is identified as being appropriate for a given patient, patients will be followed and treated in a separate 'other' (NOS) category.

With 3 disease types and 5 possible specific treatments for each, there are 15 possible treatment arms which will be under active consideration. For each of these 15, the study will be conducted as an optimal two-stage phase II trial (Simon R, Controlled Clinical Trials 10:1-10, 1989).

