In all but the arm for patients who have NSCLC and an EGFR mutation, the trial will be conducted in order to rule out an unacceptably low 10% clinical response rate (PR+CR;  $p_0=0.10$ ) in favor of a modestly high response rate of 40% ( $p_1=0.40$ ). For those 14 arms, with  $\alpha=0.05$  (probability of accepting a poor treatment=0.05) and  $\beta = 0.10$  (probability of rejecting a good treatment=0.10), the study will initially enroll 9 evaluable patients in each stratum and if 0 or 1 of the 9 have a clinical response, then no further patients will be accrued. If 2 or more of the first 9 have a response, then accrual would continue until a total of 20 patients have enrolled in that stratum. If there are 2-4 responses in 20 patients, this would be an uninterestingly low response rate in that stratum, while if there were 5 or more responses in 20 patients, then this would be sufficiently interesting to warrant further study in later trials. Under the null hypothesis (10% response rate), the probability of early termination is 77% for a given stratum.

In the arm for patients who have NSCLC and an EGFR mutation, the trial will be conducted in order to rule out an unacceptably low 30% clinical response rate (PR+CR;  $p_0=0.30$ ) in favor of a modestly high response rate of 60% ( $p_1=0.60$ ). The target is higher for these patients since a higher response rate is known to be possible for these patients. For that one arm, with  $\alpha=0.05$  (probability of accepting a poor treatment=0.05) and  $\beta = 0.10$  (probability of rejecting a good treatment=0.10), the study will initially enroll 10 evaluable patients in each stratum and if 0 to 3 of the 10 have a clinical response, then no further patients will be accrued. If 4 or more of the first 10 have a response, then accrual would continue until a total of 28 patients have enrolled in that stratum. Under the null hypothesis (30% response rate), the probability of early termination is 65% for patients in this stratum.

As feasibility is an important endpoint as well, the trial will include an early stopping rule for accrual to specific arms which are not enrolling adequate numbers of patients. After 18 months from the date the first patient enrolls on the trial in any arm, if there are arms with no more than a

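### Section 15.2 caps every stratum at 20 and the treated total at 300, but Section 15.1 takes the NSCLC/EGFR stratum to 28, so the design maximum is 308

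*Combined protocol and SAP*

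**What the plan says.** Section 15.1 defines 15 strata (three diseases by five treatments) and fixes the type of design: "For each of these 15, the study will be conducted as an optimal two-stage phase II trial".

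It then gives two sets of parameters, both with alpha 0.05 and beta 0.10:

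- **14 strata (all but NSCLC with an EGFR mutation):** 10% against 40% response. The first stage has 9 patients and stops at 0 or 1 response; otherwise "accrual would continue until a total of 20 patients have enrolled in that stratum".
- **NSCLC/EGFR stratum:** 30% against 60% response. The first stage has 10 patients and stops at 0 to 3 responses; otherwise "accrual would continue until a total of 28 patients have enrolled in that stratum".

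Section 15.2 summarises the sample size without this distinction: "With a maximum of 20 patients per stratum, up to 300 evaluable patients may be treated in specific arms". Its second paragraph uses the same total again: "In order to enroll up to 300 patients in the specific arms on the basis of molecular profiling results". It derives an enrollment of about 600 from that total. Section 3.5 gives the same overall figure: "600 patients from all participating sites and in all diseases combined".

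Two other places bear on the reading. Section 5.3 says of each arm that "it has its own eligibility criteria (Section 3) and statistical considerations (Section 15), and will be analyzed independently". Section 5.4 says of a patient who crosses over after progression: "The patient will count as a new patient to that specific arm, keeping their original patient ID number".

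**The concern.** A stratum that may accrue to 28 cannot have a maximum of 20, so Sections 15.1 and 15.2 cannot both be right. The total of 300 follows only if the NSCLC/EGFR stratum is also held to 20.

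Two things are at stake. First, a reader who took Section 15.2 literally would cap that stratum at a size that cannot deliver the error rates in Section 15.1. Second, the sample-size section is where anyone comparing planned with actual accrual will look, and it misstates both the largest stratum and the overall ceiling.

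**Working it through.** **1. Reproduce the plan's total.** 15 strata (Section 15.1) × 20 (Section 15.2) = 300. This matches the stated figure exactly.

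**2. Recompute it from Section 15.1.** 14 × 20 + 1 × 28 = 280 + 28 = 308. The difference is 8, and 8/300 = 2.7%. The whole difference lies in NSCLC/EGFR.

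**3. Check whether 20 or 28 is the intended size.** For a design that stops at r1 or fewer responses in n1 patients, and otherwise needs more than r responses in n:

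- early termination = P(X1 ≤ r1), with X1 binomial(n1, p);
- probability of a positive result = Σ over x > r1 of P(X1 = x) · P(X2 ≥ r + 1 − x), with X2 binomial(n − n1, p). This is alpha at p0 and power at p1;
- expected size under p0 = n1 + (1 − early termination) · (n − n1).

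*The 14 strata* (p0 = 0.10, p1 = 0.40, stop at ≤1 of 9, total 20, success at ≥5):

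- early termination = 0.9⁹ + 9 · 0.1 · 0.9⁸ = 0.775 (stated 77%)
- alpha 0.035, power 0.902
- expected size = 9 + 0.225 × 11 = 11.48

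A search over two-stage designs up to a total of 30 finds this to be the one with the smallest expected size under p0. The 20 is right for these strata.

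*NSCLC/EGFR* (p0 = 0.30, p1 = 0.60, stop at ≤3 of 10):

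- early termination = Σ from x = 0 to 3 of C(10,x) · 0.3ˣ · 0.7¹⁰⁻ˣ = 0.650 (stated 65%)
- expected size at a total of 28 = 10 + 0.350 × 18 = 16.31

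| Total | Success if at least | Alpha | Power | Meets 0.05 and 0.90? |
|---|---|---|---|---|
| 28 | 12 | 0.081 | 0.933 | no |
| 28 | 13 | 0.042 | 0.912 | **yes** |
| 28 | 14 | 0.019 | 0.869 | no |
| 20 | 9 | 0.098 | 0.912 | no |
| 20 | 10 | 0.045 | 0.854 | no |

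With this first stage, no total from 11 to 27 meets both error rates; 28 is the first that does, and 13 is its only qualifying cut-off. A search over two-stage designs up to a total of 40 finds 3/10 followed by 12/28 to be optimal. It also finds that the smallest total of any qualifying two-stage design is 23, so 20 would not work with a different first stage either.

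The 28 is therefore the deliberate size for this stratum. The 20 in Section 15.2 is the size for the other 14 strata, applied to all 15.

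**4. Effect on the enrollment figures.** The implied yield is 300/600 = 50%. At that yield, 308/0.5 = 616 enrolled. At the plan's 10 per month, that takes 61.6 months, against 600/10 = 60 months. This is only illustrative, because it applies an average yield to 8 places that all lie in one stratum. It does show that the approximate figures are not disturbed.

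**The case against.** The strongest reply is that very little depends on this. The operative rule for the stratum is in Section 15.1, is explicit, and is correct. No stopping rule or error rate uses the 300. Section 15.2 presents 300 as a ceiling and itself expects that far fewer patients may be enrolled if strata stop early or close for slow accrual. The treatment arms closed to recruitment on 3/22/16, so no accrual decision can change. All of this stands, and it limits the point to a correction of the text. It does not remove the contradiction, which no other section resolves.

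A second reply concerns the unit. Section 15.1 counts evaluable patients at the first stage but enrolled patients at the final total, while Section 15.2 speaks of evaluable patients. If patients who cannot be evaluated are replaced, entries could exceed 308; if they are not, the evaluable number could fall short. Crossover patients are also counted more than once. These are fair cautions about what 308 measures, but they apply equally to 300 and do not favour it. Section 5.4 already treats a crossover as a new patient in the next arm, so correcting the number while keeping the protocol's own word is consistent.

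**Conclusion.** The point holds. Section 15.2 is wrong as written on two counts: the largest stratum is 28, not 20, and the design maximum is 308, not 300. The discrepancy of 20 against 28 is the substantive one; the total moves by only 2.7%.

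The figure of 308 assumes that enrolled and evaluable refer to the same patients. It counts arm entries rather than distinct people, and it is a ceiling reached only if every stratum continues to its second stage. The consequence is confined to the stated maximum and to reporting against it. The correction is worth making but alters nothing in how the arms were designed.

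**What to change.** In Section 15.2:

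- First paragraph: give the maximum as 20 per stratum, with 28 in the NSCLC/EGFR stratum as the named exception, and change the total from 300 to 308.
- Second paragraph: change 300 to 308.

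Leave the approximate 600 enrolled and five years, and the 600 in Section 3.5, as they are.

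A separate and optional addition belongs in Section 15.1. That section gives the final decision rule for the 20-patient strata but none for the 28-patient stratum. A note, labelled as derived from the stated optimal design, could say that 4 to 12 responses in 28 is too low to be of interest and that 13 or more warrants further study. This gap exists whichever total Section 15.2 states, and the correction above does not depend on it.

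The cost is two numbers and one parenthesis, plus the optional note. No patients are added, because Section 15.1 already provides for 28.

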## **15.3 Stratification Factors**

N/A

## **15.4 Analysis of Secondary Endpoints**

In order to accomplish the secondary objective of identifying molecular profiles in patients with NSCLC, SCLC or thymic malignancies and characterize their natural histories, clinical course and response to treatment, we will follow all patients that undergo molecular profiling from the time that they are enrolled in the trial until the time of death. Demographic information such as age, gender and race will be tabulated. The frequencies of oncogenic mutations will be assessed. The exact binomial two-sided 95% confidence interval for each mutation rate will be reported.

Kaplan-Meier curves for progression free survival, duration of response, and overall survival will be calculated from the patients treated in the different treatment arms of this study (erlotinib, lapatinib, sunitinib, AZD6244, MK2206, or NOS). The results of this analysis may be compared in an informal manner to any similarly defined curves available from other published studies in comparable patients with the same disease. Expression levels of various proteins from pre- and post-treatment samples will be compared using an appropriate nonparametric test and pre-post differences between responders and non-responders using a Wilcoxon rank sum test. These latter evaluations will be considered exploratory and the resulting p-values will be presented as being exploratory and without adjustment for multiple comparisons.

For the secondary objective of determining the frequency of *EGFR* germline mutations in families with high susceptibility to lung cancer, the analyses will be performed in an exploratory manner. Hence, statistical power calculations have not been provided.

## **15.5 Reporting and Exclusions**

### **15.5.1 Evaluation of toxicity**

All patients will be evaluable for toxicity from the time of the biopsy for molecular profiling is performed. Patients who are subsequently enrolled in the NOS arm will not be evaluable for toxicity.

### **15.5.2 Evaluation of response**

All patients included in one of the experimental arms of the study must be assessed for response to treatment, even if there are major protocol treatment deviations. Each patient will be assigned one of the following categories: 1) complete response, 2) partial response, 3) stable disease, 4) progressive disease, 5) early death from malignant disease, 6) early death from toxicity, 7) early death because of other cause, or 9) unknown (not assessable, insufficient data). [Note: By arbitrary convention, category 9 usually designates the “unknown” status of any type of data in a clinical database.]

All of the patients who met the eligibility criteria for a particular treatment arm (with the exception of those who received no study medication) should be included in the main analysis of the response rate. Patients in response categories 5-9 should be considered to have a treatment failure (disease progression). Thus, an incorrect treatment schedule or drug administration does not result in exclusion from the analysis of the response rate. Precise definitions for categories 5-9 will be protocol specific.

All conclusions should be based on all eligible patients. Subanalyses may then be performed on the basis of a subset of patients, excluding those for whom major protocol deviations have been identified (e.g., early death due to other reasons, early discontinuation of treatment, major protocol deviations, etc.). However, these subanalyses may not serve as the basis for drawing conclusions concerning treatment efficacy, and the reasons for excluding patients from the analysis should be clearly reported. The 95% confidence intervals should also be provided.

## **16 HUMAN SUBJECTS PROTECTIONS**

### **16.1 Rationale for Subject Selection**

This study will be open to all individuals with advanced thoracic malignancies (lung cancer and thymic malignancies) regardless of gender, ethnicity, or race provided that the aforementioned inclusion and exclusion criteria are met. For safety reasons, only pregnant women and children are excluded from this study. This study will be recruited through internal referral, our local physician referral base, and through various cancer information hotlines (i.e., Clinical Studies Support Center, [name]). This is a trial designed to evaluate the efficacy of different targeted therapies in patients with advanced thoracic malignancies. Patients should realize that we are hopeful that they may gain benefit from this study, but there is no objective evidence to support our optimism at this time. Subjects from both genders and all racial/ethnic groups are eligible for this study if they meet the eligibility criteria outlined in Section 3. To date, there is no information that suggests that differences in drug metabolism or disease response would be expected in one ethnic group compared to another. Efforts will be made to extend accrual to each representative population, but in this preliminary study, a balance must be struck between

patient safety considerations and limitations on the number of individuals exposed to potentially toxic and/or ineffective treatments on the one hand and the need to explore racial/ethnic aspects of clinical research on the other hand. If differences in outcome that correlate to ethnic identity are noted, accrual may be expanded or a follow-up study may be written to investigate those differences more fully.

## **16.2 Justification for Exclusions**

Due to lack of knowledge of the effects of most or all of the targeted agents included in this trial on the fetus or on infants, as well as the possibility of teratogenic effects, pregnant and nursing women will be excluded from this trial. Patients with unstable or serious medical conditions (ongoing or active infection, symptomatic congestive heart failure (AHA Class II or worse), unstable angina pectoris, cardiac arrhythmia, or psychiatric illness/social situations that would limit compliance with study requirements) are excluded due to the possibility that the agents used may worsen their condition and the likelihood that the underlying condition may obscure the attribution of adverse events with respect to protocol therapy.

### **16.2.1 Participation of Children**

Patients under the age of 18 will be excluded from study due to the low occurrence of these oncologic histologies in the pediatric population. In addition, the risk of exposure to an investigational agent without proven benefit in the targeted histologies supports excluding children until additional safety and efficacy data is available. Patients under the age of 18 will be excluded from germline mutation testing because of the infrequency of lung cancer in this age group and because the results would not influence the medical management of individuals under the age of 18.

## **16.3 Participation of Subjects Unable to Give Consent**

Adults unable to give consent are excluded from enrolling in the protocol. However, re-consent may be necessary and there is a possibility, though unlikely, that subjects could become decisionally impaired. For this reason and because there is a prospect of direct benefit from research participation (section 16.4), all subjects  $\geq$  age 18 will be offered the opportunity to fill in their wishes for research and care, and assign a substitute decision maker on the “NIH Advance Directive for Health Care and Medical Research Participation” form so that another person can make decisions about their medical care in the event that they become incapacitated or cognitively impaired during the course of the study. Note: The PI or AI will contact the NIH Ability to Consent Assessment Team (ACAT) for evaluation as needed for the following: an independent assessment of whether an individual has the capacity to provide consent; assistance in identifying and assessing an appropriate surrogate when indicated; and/or an assessment of the capacity to appoint a surrogate. For those subjects that become incapacitated and do not have pre-determined substitute decision maker, the procedures described in NIH HRPP SOP 14E for appointing a surrogate decision maker for adult subjects who are (a) decisionally impaired, and (b) who do not have a legal guardian or durable power of attorney, will be followed.

